6.2 Dose Modifications for Non-Hematological Toxicity

Patients who experience Grade 3 prolonged QTc (\geq 501 msec) will be removed from protocol therapy.

Patients who experience dose-limiting toxicity at dose levels 1 or 2 but do not have evidence of disease progression may continue to receive therapy modified as described below.

Patients who experience DLT at dose level 0 will not receive further therapy on study

- 6.2.1 Patients who have any dose-limiting non-hematological toxicity (as defined in section 5.5.2) that returns to eligibility criteria within 7 days after the planned start of the next treatment cycle may continue on study but should receive subsequent doses at the next lower dose level of eribulin. If non-hematologic Grade 3 or 4 toxicities other than those listed in Section 5.5.2 recur at a reduced dose, the patient must be removed from protocol therapy.
- 6.2.2 Patients who have any Grade 3 or 4 non-hematological toxicity that does not resolve to eligibility criteria by 7 days after the planned start of the next treatment cycle must be removed from protocol therapy.

7. ADVERSE EVENTS: LIST AND REPORTING REQUIREMENTS

7.1 Definitions

Adverse Event: Any unfavorable and unintended sign (including abnormal laboratory finding), symptom, or disease temporally associated with the use of a medical treatment or procedure, regardless of whether it is considered related to the medical treatment or procedure (attribution of unrelated, unlikely, possible, probable or definite).

Serious Adverse Event: An adverse event or suspected adverse reaction is considered "serious" if, in the view of the investigator, it results in any of the following outcomes: Death, a life-threatening adverse event, inpatient hospitalization or prolongation of existing hospitalization, a persistent or significant incapacity or substantial disruption of the ability to conduct normal life functions, or a congenital anomaly/birth defect. Important medical events that may not result in death, be life-threatening, or require hospitalization may be considered serious when, based upon appropriate medical judgment, they may jeopardize the patient or subject and may require medical or surgical intervention to prevent one of the outcomes listed in this definition.

Unanticipated Problems: Include adverse events which in the opinion of the principal investigator are both unexpected and probably or definitely related to the intervention / drug or device, any unforeseen development that potentially increases the likelihood of harm to participants or others in the future, information that indicates a change to the risks or potential benefits of the research or an actual unforeseen harmful or unfavorable occurrence to participants or others that relates to the research protocol (injuries, psychological events, drug errors).

Other Reportable Adverse Events: Include death unrelated to study treatment if occurring within 30 days of the last study treatment, death at least possibly related to study treatment at any time point, secondary malignancy, pregnancy, fetal death, and neonatal death.

Adverse event (AE) monitoring and reporting is a routine part of every clinical trial. The following list of AEs (Section 7.2) and the characteristics of an observed AE (Section 7.3) will determine whether the event requires expedited reporting (via Medwatch Forms) **in addition** to routine reporting.

7.2 Expected Toxicities

Onset	Common:	Occasional:	Rare:
	>20% of patients	<20% of patients	<10% of patients
Immediate: hours to days	Nausea, vomiting		anaphylaxis
Prompt: days to weeks	Anorexia, weight loss, constipation, fatigue, pain, myelosuppression, increased LFTs, neuropathy,	Diarrhea, headache, increased creatinine, cough, dyspnea	Vertigo, hypertension, QT prolongation, venous thromboembolism, hand- foot syndrome, rash, abdominal pain, mucositis, edema, pancreatitis, electrolyte abnormality, hyperglycemia, anxiety, depression, insomnia, dizziness, dysgeusia, pharyngolargyngeal pain, conjunctivitis,
Delayed: weeks to months	Alopecia		

7.2.1 Adverse Events List for Eribulin

7.2.2 Adverse Events List for Irinotecan

Onset	Common:	Occasional:	Rare:		
	>20% of patients	<20% of patients	<5% of patients		
Immediate: hours to	Nausea, vomiting,	Constipation, headache,	Anaphylaxis, dehydration		
days	anorexia, fever,	diarrhea	with dizziness and		
	asthenia, cholinergic		hypotension, bradycardia,		
	symptoms: (rhinitis,		dyspnea and cough,		
	increased salivation,		disorientation/confusion,		
	miosis, lacrimation,		somnolence, pain at infusion		
	diaphoresis, flushing		site		
	and intestinal				
	hyperperistalsis that can				
	cause abdominal				
	cramping and early				
	diarrhea)				
Prompt: days to	Diarrhea, neutropenia,	Anemia, rash,	Colitis, renal failure		
weeks	alopecia, eosinophilia,	dyspepsia,	(secondary to severe		
	elevations in	thrombocytopenia	dehydration),		
	transaminases, alkaline		thromboembolic events,		
	phosphatase, bilirubin,		ileus		
	mucositis, infection				
Delayed: weeks to			Pneumonitis		
months					
Unknown frequency	Fetal toxicities and teratogenic effects of irinotecan have been noted in animals at				
and timing	doses similar or less than those used in humans. Toxicities include: decreased				
	skeletal ossification, multiple anomalies, low birth weight and increased fetal				
	mortality. It is not known if irinotecan is excreted into breast milk but it is				
	excreted into rat milk.	excreted into rat milk.			

For a comprehensive list of adverse events please refer to the package insert.

7.3 Adverse Event Characteristics

- **CTCAE term (AE description) and grade:** Adverse events that occur while the patient is on study will need to be recorded. Please see below for specific reporting requirements. Each investigative site will be responsible for maintaining an AE log that captures all AEs and SAEs. All Adverse Events will be recorded as "related" or "not related" in the AE log. Each site will also need to report all SAEs that occur at that institution to their respective IRB as per their IRB policy in addition to the protocol requirements. A copy of the CTCAE version 4.0 can be downloaded from the CTEP web site http://ctep.cancer.gov/protocolDevelopment/electronic_applications/ctc.htm.
- **Attribution** of the AE:
 - Definite The AE *is clearly related* to the study treatment.
 - Probable The AE *is likely related* to the study treatment.
 - Possible The AE may be related to the study treatment.
 - Unlikely The AE is doubtfully related to the study treatment.
 - Unrelated The AE is clearly NOT related to the study treatment.

7.4 Expedited Adverse Event Reporting

7.4.1 Investigators **must** report to the study PI's and coordinating center (CHCO) any serious adverse event (SAE) that occurs after the initial dose of study treatment, during treatment, or within 30 days of the last dose of treatment on the standardized SAE form.

Note: If subject is in Long Term Follow Up, death is reported at continuing review.

Note: Abnormal laboratory values are not considered medical events, unless determined to be causative of SAE by the investigator or grade 5.

Expedited reporting to DSMC	Expedited reporting to FDA	Non- expedited AE	Form	IRB
All SAEs (severity of adverse event is Grade 3, 4 or 5)	Suspected AE that is serious and unanticipated (not listed in IB or consent)	CRF and DSMC reporting only	Voluntary Medwatch 3500 for serious and unanticipated CRF for all AEs, including SAEs	Yes if it meets the IRB reporting requirements: If reportable event, please send copy of IRB report to CHCO

7.4.2 The following table outlines the required forms and reporting structure for clinical trials.

7.5 Routine Adverse Event Reporting

All Adverse Events (Grades 1-5) **must** be recorded on case report forms and reported to the overall PI in routine study data submissions. **AEs reported through expedited processes (e.g., reported to the IRB, FDA, etc.) must** also be reported in routine study data submissions. All Adverse Events will be recorded as "related" or "not related" in the AE log. Depending on the grade of each AE, it will need to be reported to CHCO within 5 calendar days or 24 hours. Please refer to the table below for AE reporting time lines.

	When to report AEs to CHCO							
Attribution	Gr. 1 and 2 AE Expected and Unexpected	Gr. 3 AE Expected and Unexpected	Gr. 4 AE Expected and Unexpected	Gr. 5 AE Expected and Unexpected				
Unrelated Unlikely	Record in AE Log	5 calendar days	5 calendar days	24 hours				
Possible Probable Definite	Record in AE Log	5 calendar days	5 calendar days	24 hours				

8. PHARMACEUTICAL INFORMATION

A list of the adverse events and potential risks associated with the investigational or commercial agents administered in this study can be found in Section 7.1.

- 8.1 Eribulin mesylate [11,15:18,21:24,28-Triepoxy-7,9-ethano-12,15-methano-9H,15H-furo[3,2-i]furo[2",3":5,6]pyrano[4,3-b][1,4]dioxacyclopentacosin-5(4H)-one, 2-[(2S)-3-amino-2-hydroxypropyl]hexacosahydro-3-methoxy-26-methyl-20,27-bis(methylene)-, (2R,3R,3aS,7R,8aS,9S,10aR,11S,12R,13aR,13bS,15S,18S,21S,24S,26R,28R,29aS)-, methanesulfonate (salt), Halavan^{TM®}]
 - 8.1.1 Dosage and Route of Delivery: Since this a Phase I study, dosage will be defined by the dose escalation scheme. To administer the drug, it will be aseptically withdrawn from the single-use vial and administer undiluted or diluted in 0.9% Sodium Chloride Injection, USP intravenously over 2 to 5 minutes.
 - 8.1.2 Adjustment of Dosing: This is defined in section 6.1 and 6.2 of the protocol
 - 8.1.3 Source and pharmacology: Eribulin mesylate is a non-taxane microtubule dynamics inhibitor. Eribulin mesylate is a synthetic analogue of halichondrin B, a product isolated from the marine sponge Halichondria okadai.

Eribulin inhibits the growth phase of microtubules without affecting the shortening phase and sequesters tubulin into nonproductive aggregates. Eribulin exerts its effects via a tubulin-based antimitotic mechanism leading to G2/M cell-cycle block, disruption of mitotic spindles, and, ultimately, apoptotic cell death after prolonged mitotic blockage.

The pharmacokinetics (PK) of eribulin is linear with a mean elimination half-life of approximately 40 hours, a mean volume of distribution of 43 L/m^2 to 114 L/m^2 and mean clearance of 1.16 $L/hr/m^2$ to 2.42 $L/hr/m^2$ over the dose range of 0.25 mg/m² to 4.0 mg/m². The human plasma protein binding of eribulin at concentrations of 100 ng/mL to 1,000 ng/mL ranges from 49% to 65%. Eribulin exposure after multiple dosing is comparable to that following a single dose. No accumulation of eribulin is observed with weekly administration.

Unchanged eribulin was the major circulating species in plasma following administration of 14C-eribulin to patients. Metabolite concentrations represented < 0.6% of parent compound, confirming that there are no major human metabolites of eribulin. Cytochrome P450 3A4 (CYP3A4) negligibly metabolizes eribulin in vitro.

Eribulin is eliminated primarily in feces unchanged. After administration of 14Ceribulin to patients, approximately 82% of the dose was eliminated in feces and 9% in urine. Unchanged eribulin accounted for approximately 88% and 91% of the dose in feces and urine, respectively.

- 8.1.4 Formulation & Stability: Eribulin mesylate injection, 1 mg/2 mL, in a single-use vial. One vial per carton. Store at 25°C (77°F); excursions permitted to 15°-30°C (59°-86°F). Do not freeze. Store the vials in their original cartons.
- 8.1.5 Guidelines for Administration: See Treatment and Dose Modifications sections of the protocol. The FDA-approved dose of Eribulin as a single agent in adults is 1.4 mg/m² administered intravenously over 2 to 5 minutes on Days 1 and 8 of a 21-day cycle.
- 8.1.6 Toxicity: In Phase 3 studies, the most common treatment-emergent adverse events noted are described. Over half of patients experienced neutropenia or leukopenia, and 20% had anemia. One third of patients complained of asthenia or fatigue. Nausea was observed in 22% and diarrhea in only 14%. Peripheral neuropathy was observed in 27%. One third of patients experienced alopecia. Of the almost 2000 patients exposed in completed clinical studies as of May 2013, 367 patients had related serious adverse events. The most frequent treatment-related SAEs were febrile neutropenia (3.3%), neutropenia (1.9%), and pyrexia (1.2%).
- 8.1.7 Supplier: Eribulin is commercially available by Eisai. See package insert or IB for more detailed information.
- **8.2** **Irinotecan** [CPT-11,Camptothecin-11,7-ethyl-10-(4-[1-piperidino]-1-piperidino)-carbonyloxy-camptothecin), Camptosar®], NSC #616348
 - 8.2.1 Dosage and Route of delivery: Irinotecan will be given orally daily for days 1-5 of each 21 day cycle. The dose will be 90 mg/m²/dose. On day 1 of each cycle, it

will be given at least 15 minutes after the eribulin. For oral use, the appropriate volume of irinotecan solution (20 mg/ml) is drawn up undiluted into a plastic oral syringe. Each dose is to be mixed with juice (crangrape, cranapple, cranberry, or other "cran" juice) immediately before administration. The oral syringes containing undiluted irinotecan are stable for 21 days when stored in a refrigerator. Irinotecan has a very unpleasant flavor, and so the juice will be used to mask the drug taste (Appendix D). See protocol for premedication and supportive care measures.

If emesis occurs within 20 minutes of taking a dose of irinotecan, then the dose may be repeated once. If emesis occurs after 20 minutes, the dose should not be repeated. Instructions for administration of oral irinotecan are included in Appendix D and a copy of Appendix B, outlining potential drug interactions with irinotecan, should be given to the patient.

- 8.2.2 Adjustment of Dosing: This is defined in section 6.1 and 6.2 of the protocol
- 8.2.3 Source and pharmacology: Irinotecan is a semisynthetic water-soluble analog of camptothecin (a plant alkaloid isolated from Camptotheca acuminata). Irinotecan is a prodrug that requires conversion, by the carboxylesterase enzyme to the topoisomerase-I inhibitor, SN-38 in order to exert anti-tumor activity. SN-38 is approximately 1000 times more potent than irinotecan. Camptothecins interact specifically with the enzyme topoisomerase I which relieves torsional strain in DNA by inducing reversible single-strand breaks. Irinotecan and its active metabolite SN-38 bind to the topoisomerase I-DNA complex and prevent religation of these single-strand breaks. Current research suggests that the cytotoxicity of irinotecan is due to double-strand DNA damage produced during DNA synthesis when replication enzymes interact with the ternary complex formed by topoisomerase I, DNA, and either irinotecan or SN-38. Renal excretion is a minor route of elimination of irinotecan. The majority of the drug is metabolized in the liver. SN- 38 is conjugated to glucuronic acid and this metabolite has no anti-tumor activity. The extent of conversion of SN-38 to its glucuronide has been inversely correlated with the risk of severe diarrhea, because the other major route of SN-38 excretion is biliary excretion by canalicular multispecific organic anion transporter (cMOAT) which presumably leads to mucosal injury. In addition, APC and NPC are oxidative metabolites of irinotecan dependent on the CYP3A4 isoenzyme. After intravenous infusion of irinotecan in humans, irinotecan plasma concentrations decline in a multiexponential manner, with a mean terminal elimination half-life of about 6 to 12 hours. The mean terminal elimination half-life of the active metabolite SN-38 is about 10 to 20 hours. Irinotecan is 30% to 68% bound to albumin and SN-38 is approximately 95% bound to albumin.
- 8.2.4 Formulation & Stability: Each mL of irinotecan injection contains 20 mg irinotecan (on the basis of the trihydrate salt); 45 mg sorbitol; and 0.9 mg lactic acid. When necessary, pH has been adjusted to 3.5 (range, 3.0 to 3.8) with sodium

hydroxide or hydrochloric acid. Irinotecan is available in single-dose amber glass vials in 40mg (2ml) and 100mg (5ml). Store at controlled room temperature 15° to 30°C (59° to 86°F). Protect from light. It is recommended that the vial (and backing/plastic blister) should remain in the carton until the time of use.

8.2.5 Guidelines for Administration: See Treatment and Dose Modifications sections of the protocol.

For oral use, the appropriate volume of irinotecan solution (20 mg/ml) is drawn up undiluted into a plastic oral syringe. Each dose is to be mixed with juice (crangrape, cranapple, cranberry, or other "cran" juice) immediately before administration. The oral syringes containing undiluted irinotecan are stable for 21 days when stored in a refrigerator. Irinotecan has a very unpleasant flavor, and so the juice will be used to mask the drug taste (Appendix D). See protocol for premedication and supportive care measures.

Cefixime or an available equivalent antibiotic will be used as diarrheal prophylaxis. Initiation of antibiotic treatment at least two days prior to the start of irinotecan is recommended. This antibiotic therapy should continue until 2 days after the last dose of irinotecan.

Premedication with a 5-HT₃ antagonist, like ondansetron is recommended 30 minutes prior to daily irinotecan doses. Aprepitant is an inducer, a moderate inhibitor, and substrate of CYP3A4 and should not be used as an anti-emetic.

If emesis occurs within 20 minutes of taking a dose of irinotecan, then the dose may be repeated once. If emesis occurs after 20 minutes, the dose should not be repeated. Instructions for administration of oral irinotecan are included in Appendix C.

8.2.6 Supplier: Irinotecan is commercially available. See package insert for more detailed information.

8.3 Cefixime [Suprax®]

- 8.3.1 Source and pharmacology: Cefixime is a third generation cephalosporin antibiotic for oral administration that inhibits bacterial cell wall synthesis by binding to one or more of the penicillin-binding proteins and interfering with the final transpeptidation step of peptidoglycan synthesis. Its spectrum of activity is similar to other third generation agents, including Enterobacteriaceae, and β-lactamase producing H. influenzae and N. gonorreae, and Staph. aureus. It is excreted primarily by the kidney. It has a serum half-life of approximately 3-4 hours.
- 8.3.2 Formulation & Stability: Cefixime is available in scored 200 mg and 400 mg film coated tablets, and in a powder for oral suspension, which when reconstituted, provides 100mg/5ml. The powder for oral suspension is strawberry flavored and

contains sodium benzoate, sucrose, and xanthan gum.

8.3.3 Guidelines for Administration: Given orally at 400 mg daily.

8.3.4 Supplier: Commercially available.

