[name], MS [name] [contact] Email: [contact]

Responsible Research Nurse:

[name], CPON, CCRP Children's Hospital Colorado [name] [contact] Email: [contact]

Study Coordinator:

[name], CPON, CCRP Children's Hospital Colorado [name] [contact] E-mail: [contact]

Responsible Data Manager:

[name], BS Children's Hospital Colorado [name] [contact] E-mail: [contact]

Commercially Available Agents:

Eribulin (Halaven®, Eisai Inc., Woodcliff Lake, NJ) Irinotecan (Camptosar®, Pfizer, New York City, NY)

IND Sponsor: Exempt from IND requirement

Protocol Version # / Version Date: Version 3.0 / March 22, 2017

SUMMARY

This Phase I trial will establish the recommended phase II dose of eribulin in combination with fixed doses of oral irinotecan in adolescents and young adults with relapsed or refractory solid tumors. Eribulin will be administered intravenously on days 1 and 8 of a 21-day cycle, while irinotecan will be administered orally on days 1-5. The oral antibiotic cefixime will be used to reduce irinotecan-associated diarrhea, starting two days prior to each cycle and continuing through day 8. Patients will be assigned an eribulin dose level at the time of enrollment using a 3 + 3 Phase I design, and there will be no intrapatient dose escalation. Once the RP2D is defined, there will be 10 patients enrolled in a dose expansion cohort.

Day	Cefixime	Eribulin	Oral Irinotecan
-1	Х		
0	Х		
1	Х	Х	Х
2	Х		Х
3	Х		Х
4	Х		Х
5	Х		Х
6	Х		
7	Х		
8	Х	Х	
9-19			
20	Х		
21	Х		
NEXT CYCLE			

Treatment Schema

Dose Escalation Schedule				
	Dos	se		
Dose Level	Oral Irinotecan (mg/m ² /day x 5)	Eribulin (mg/m ² /dose)		
Level 0	90	0.8		
STARTING DOSE: Level 1	90	1.1		
Level 2	90	1.4		

TABLE OF CONTENTS

COM	IRB #1	5-0659	1
SUM	MARY		4
1.	OBJE	ECTIVES	7
	1.1	Primary Objectives	7
	1.2	Secondary Objectives	7
2.	BAC	KGROUND	7
	2.1	Introduction	7
	2.2	Eribulin	7
	2.3	Irinotecan	9
	2.4	Rationale for Combining Eribulin and Irinotecan	11
	2.5	Correlative Studies Background	11
3.	PATI	ENT SELECTION	12
	3.1	Eligibility Criteria	12
	3.2	Exclusion Criteria	13
	3.3	Inclusion of Women and Minorities	14
4.	REG	ISTRATION PROCEDURES	15
	4.1	Enrollment Guidelines	15
	4.2	Compliance with Laws and Regulations	15
5.	TREA	ATMENT PLAN	16
	5.1	Enrollment and Screening Process	16
	5.2	Agent Administration	16
	5.3	Supportive Care	

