Pharmacokinetic data: Irinotecan is converted into its active metabolite SN-38 in the liver by carboxylesterase enzymes [48]. SN-38 is subsequently converted to SN-38 glucuronide by uridine diphosphate glucuronosyltranferases (UDG). Although the majority of irinotecan is metabolized into SN-38 under normal circumstances, a small minority is converted into two minor metabolites by cytochrome P450 isoenzyme CYP3A4. Predictably, inducers of the CYP3A4 isoenzyme have been shown to lead to increased clearance of irinotecan and reduced levels of SN-38 [49, 50]. Use of CYP3A4 inducers should be avoided due to concerns for decreased efficacy of irinotecan.

Toxicity data: The dose limiting toxicities of irinotecan administered intravenously on adult schedules of once every 1-3 weeks are myelosuppression and diarrhea. When irinotecan is administered on a protracted schedule as done in pediatrics, myelosuppression is substantially

reduced while diarrhea remains the dose-limiting toxicity [51-53]. The addition of cephalosporin prophylaxis to various treatment regimens of irinotecan has increased the tolerability of protracted irinotecan by significantly decreasing the incidence of diarrhea, allowing for the escalation of the maximum tolerated dose (MTD) [44, 45, 54]. The active metabolite SN-38 is thought to act locally in the gastrointestinal tract, directly injuring the intestinal mucosa and leading to a secretory diarrhea [55]. Cephalosporins ameliorate irinotecan-associate diarrhea by limiting conversion of the inactive glucuronidated SN-38 to active SN-38 by glucuronidase producing enteric bacteria. Pediatric regimens using cephalosporins have shown significant reduction in severe diarrhea when antibiotics are started a few days prior to irinotecan, and continued for three days past the fifth chemotherapy day. [44, 45, 54]

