5.3.3 Concomitant Medications

Eribulin has been associated with prolonged QTc, so medications that prolong QTc should be avoided when possible. A list of medications that prolong QTc is provided in Appendix C.

5.3.4 Supportive Care

Appropriate antibiotics, blood products, antiemetics, fluids, and general supportive case are to be used as necessary.

5.3.5 Prophylaxis for Irinotecan-Associated Diarrhea

Cefixime or an available equivalent antibiotic will be used to reduce irinotecan-associated diarrhea as previously mentioned [44, 45]. Antibiotic treatment should start at least two days prior to the start of irinotecan. This antibiotic therapy should continue until 3 days after the last dose of irinotecan.

5.3.6 Concomitant Medications for Diarrhea and Abdominal Cramping

Patients and their families will be instructed to contact their physician if diarrhea occurs. Any patient who develops diarrhea or abdominal cramping within the first 4 hours after oral administration of irinotecan should receive atropine intravenously at a dose of 0.01 mg/kg (maximum 0.4 mg). This so-called "early onset diarrhea" is often presaged by cholinergic manifestations such as diaphoresis and abdominal cramping. Because patients are treated with irinotecan over multiple days, it may be difficult to distinguish immediate from delayed diarrhea. Patients with presumed immediate diarrhea who do not improve with atropine, or patients who develop diarrhea more than 4 hours after receiving irinotecan, should be given treatment with oral loperamide for late onset diarrhea as outlined below.

All patients will receive a copy of instructions for the use of loperamide if/when diarrhea occurs (Appendix D). Each family will be provided with this antidiarrheal medicine with instructions to start at the first episode of poorly formed or loose stools, or at the earliest onset of bowel movements more frequent than normally expected for the patient.

Loperamide (1 mg/5 ml or 1 caplet = 2 mg) dosing guidelines for diarrhea: Weight \geq 43 kg (\geq 95 pounds): Take 4 teaspoonfuls or 2 caplets after the first loose stool, followed by two teaspoonfuls or one caplet every two hours as needed. Weight 20 kg to 43 kg (\leq 94 pounds): Take 2 teaspoonfuls or 1 caplet after the first loose stool, followed by one teaspoonful or one-half caplet every 2 hours as needed.

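### Section 8.2.5 stops the antibiotic on day 7; every other current instruction that gives a stop day puts it on day 8

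*Combined protocol and SAP*

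**What the plan says.** Section 8.2.1 fixes the chemotherapy days: "Irinotecan will be given orally daily for days 1-5 of each 21 day cycle".

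The protocol then says when the antibiotic stops in several places:

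- Section 8.2.5, in the irinotecan part of the pharmaceutical information: "This antibiotic therapy should continue until 2 days after the last dose of irinotecan".
- Section 5.3.5, the supportive care instruction on prophylaxis for irinotecan-associated diarrhea: "This antibiotic therapy should continue until 3 days after the last dose of irinotecan". On the start of the course it says: "Antibiotic treatment should start at least two days prior to the start of irinotecan".
- The Summary describes cefixime as "starting two days prior to each cycle and continuing through day 8". The schema below it marks cefixime on day 8 and leaves days 9 to 19 blank.
- The therapy delivery map in Section 5.2 lists cefixime from day -1 to day 8 and has a cefixime dose entry in the day 8 row.
- Section 2.3, as background, reports that earlier pediatric regimens reduced severe diarrhea when the antibiotic was "continued for three days past the fifth chemotherapy day".

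Section 8.3.3 (cefixime) gives the daily dose and no stop day. The Appendix F diary has a cefixime column for every day up to 21 and prints no stop day either.

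**The concern.** Sections 5.3.5 and 8.2.5 both tell sites when to stop the same drug, and they give different answers. The two sentences are identical apart from the number of days. Both are current instructions, and neither is presented as an alternative to the other.

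The prophylaxis matters to this regimen. Section 2.3 says that with protracted dosing "diarrhea remains the dose-limiting toxicity". It also explains that cephalosporin cover is what allowed the oral irinotecan dose to be raised to the 90 mg/m² used here. A site reading only Section 8.2.5 would shorten that cover by a day in each cycle. It would be complying with one section of the protocol and departing from another, so whether a day 7 stop is a protocol deviation would be unclear.

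**Working it through.** The check is day arithmetic: stop day = last irinotecan day + stated number of days after it.

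**Input.** The last irinotecan dose is on day 5 (Section 8.2.1, and the same in the Summary schema and the Section 5.2 map).

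**The plan's own figure first.** Section 5.3.5: 5 + 3 = day 8. This reproduces the day 8 given in the Summary, the schema and the delivery map.

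**Section 8.2.5.** 5 + 2 = day 7.

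| Place | Rule | Stop day |
|---|---|---|
| Summary and schema | day 8 stated or marked | 8 |
| 5.2 delivery map | day -1 to day 8 | 8 |
| 5.3.5 | last dose + 3 days | 5 + 3 = 8 |
| 2.3 (background on earlier regimens) | chemotherapy day 5 + 3 days | 5 + 3 = 8 |
| 8.2.5 | last dose + 2 days | 5 + 2 = 7 |

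**Size.** 8 − 7 = 1 day per cycle. Cover after the last irinotecan dose is 2 days instead of 3. Section 5.7 allows up to 17 cycles, so the ceiling per patient is 1 × 17 = 17 days. That would require all 17 cycles to be given and Section 8.2.5 to be followed in each. The useful figure is one day per cycle. I give no total for the antibiotic dose, because the start of the course is a minimum lead time and an equivalent antibiotic is allowed.

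**Can the wording be reconciled?** If the stop were read as excluding the named day, both sentences would move back by one day and still differ by one. Only the inclusive reading makes Section 5.3.5 agree with the Summary, schema and map, and under that reading Section 8.2.5 gives day 7.

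**Which sentence is wrong?** Every other operative statement of a stop day gives day 8, and the background describes the same duration. Section 8.2.5 also sends readers to Appendix C for irinotecan administration. Appendix C is the list of QTc-prolonging drugs, and the administration guidelines are in Appendix D, as Section 8.2.1 correctly says. This suggests that Section 8.2.5 was not kept in step with the rest of the protocol, and that the shorter duration is a slip.

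**The case against.** The best defense is that few sites would act on the sentence. Section 8.2.5 is a secondary restatement within a drug monograph. It opens with "See Treatment and Dose Modifications sections of the protocol" and later refers readers back to the protocol for supportive care, and those sections lead to day 8. The Section 5.2 delivery map is a per-patient worksheet with columns for the date due and the date given, and it has a cefixime entry on day 8. Day 8 is also an eribulin day. A site would have to leave its own dosing sheet to stop on day 7. All of this stands, and it makes the error unlikely to be acted on. It does not make the sentence correct: after pointing to the treatment text, Section 8.2.5 gives a stop rule that contradicts it.

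A second objection is that no harm is shown. The documents give no comparison of 2 with 3 days of cover after irinotecan. That also stands, and no clinical effect is asserted.

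A third concerns dose-limiting toxicity. Section 5.5.2 excludes Grade 3 diarrhea, whatever its duration, when the patient did not receive the supportive care set out in Section 5.3, cefixime included. A cycle 1 patient who stopped on day 7 under Section 8.2.5 could raise a question under that exclusion. However, Section 5.5.2 names Section 5.3 as its standard, and that text gives day 8. A dispute would also need attributable Grade 3 diarrhea lasting more than 3 days in that patient. The documents offer no basis for estimating how likely this is, so it does not raise the severity.

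**Conclusion.** The concern holds. Section 8.2.5 stops the prophylaxis on day 7, while the Summary, the schema, Section 5.2 and Section 5.3.5 stop it on day 8. The discrepancy is one day per cycle. It rests only on irinotecan ending on day 5, which the protocol states, and on reading both sentences in the same way.

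It is minor. It is a wrong instruction in current text about prophylaxis against a toxicity the protocol treats as dose-limiting, but the dosing worksheet and the cross-references make it unlikely to be followed. It does not touch the design or the analysis.

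**What to change.** In Section 8.2.5, change the number of days after the last irinotecan dose from 2 to 3 and add in brackets that this means through day 8. The stop day needs no change in any other section.

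The cost is a one-digit correction and a short day reference, made with the next amendment. Sample size, the escalation rule and the analysis are unaffected.
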